# **Trial Evaluation Protocol**

[Schwartz Rounds]
Evaluator (institution): CASCADE, Cardiff University Principal investigator(s): [name]

Template last updated: June 2019

Intervention Developer	Point of Care Foundation	
Delivery Organisations	Local authorities in England and the Point of Care Foundation	
Evaluator	Cascade	
Principal Investigator	[name]	
Protocol Author(s)	[name] and [name]	
Type of Trial	Randomised control trial	
Age or Status of Participants	Members of local authority staff working for children's services departments	
Number of Participating Local Authorities	Eleven	
Number of Children and Families	None	
Primary Outcome(s)	Psychological well-being of staff	
Secondary Outcome(s)	Sickness-related absence, psychological well-being of staff	
Contextual Factors	Schwartz Rounds have been evaluated in health settings in the UK and the USA. This trial will help evaluate their impact in the context of children's services in the UK. Midway through the trial, the UK underwent the Covid-19 pandemic, and associated lockdowns.	
Version	V 2.0 published December 2020. Details are provided of how this differs from the previous published version on page 3.	

# **Background and Problem Statement**

This protocol supersedes a previous protocol published in March 2019. This is due to the addition of more local authorities to the trial in a second phase of data collection in order to increase statistical power after there were challenges with initial recruitment. In addition, in phase two there has been a significant change in the mode of delivery of the intervention. Due to the Covid-19 pandemic, rounds cannot be delivered face-to-face and so the five new authorities to join the trial will deliver their rounds virtually. The key changes in this version of the protocol compared to the original version are as follows:

Section	Changes made
Protocol authors (p. 1)	This second version was written by [name] and [name]
,	(the previous version by [name] and [name])
Secondary outcomes (p. 1)	Previously, we were intending to collect data from local authorities about
	staff retention rates, however we were unable to collect this data and so
	we will no longer be measuring this outcome (staff retention).
Contextual factors (p. 1)	In this version, we have added in a reference to the Covid-19 pandemic
	as a significant contextual factor, necessitating a change in the mode of
	delivery for the intervention (from face-to-face, to virtual).
Background and problem	Updated to reflect the inclusion of five additional local authorities, and the
statement (p. 3-4)	use of virtual Schwartz Rounds, compared to face-to-face rounds.
Intervention and theory of	Updated to reflect the inclusion of five additional local authorities and the
change (p. 5-6)	delivery of rounds virtually due to the Covid-19 pandemic and associated
	lockdowns and social distancing measures.
	Information added about the similarities and differences between rounds
	delivered face-to-face and virtually. These differences and similarities
	have been identified by the provider of the intervention (Point of Care
	Foundation).
Primary hypothesis (p. 8)	The primary hypothesis has been modified, to say that levels of stress
	(measured by the GHQ-12) will be lower in the intervention group,
	compared to the control group, but not that levels of stress will necessarily
	decrease for either group (this is to take account of the impact of the
	pandemic on working conditions, which may have increased overall levels
	of stress for local authority staff).
Secondary hypothesis (p.	The third secondary hypothesis has been modified, so that while we will
9)	still compare rates of sickness-related absence between the two groups,
	we no longer specify that this will take place during the 6 to 8 months of
	the trial period. This is because there is too much variation between the
D : ( 10)	authorities in terms of the length of the trial period.
Design (p. 10)	This section now notes that the intervention is delivered to groups of staff.
Data collection points (p.	Removed a reference to the collection of administrative data on sickness-
12)	related absence. We were unable to collect these data from the original
	six local authorities in the study as planned and will now rely on self-report
	data instead.
	Updated versions of the survey now request work email addresses (as an
	optional response); this is to aid with matching between different data
	collection instruments.
	Information about observations of the intervention, sessional feedback
	questionnaires, focus groups and interviews have been moved to the
Pandamination (n. 12, 12)	'Implementation and Process Evaluation' section.
Randomisation (p. 12 – 13)	More details added to explain how we randomised staff between the two
Sample size calculations	groups.  Updated to include the five additional local authorities and to reflect the
(p. 14)	impact of different response/attrition rates.
Outcome measures (p. 15)	Information added in relation to the five additional local authorities, and
Culcome measures (p. 15)	about the collection of T2 data in March and April 2021. We are also now
	intending to collect data about staff absence based on self-report, rather
	than administrative data (as this proved too difficult to collect in phase
	one).
Primary analysis (p. 15)	Clarification that our hypothesis is one-sided.
· ······ary arranyono (p. 10)	Claimedach that our hypothesis is one sided.

Exploratory analysis (p. 16)	Additional information added about our intention to look for possible differences between attending face-to-face and virtual rounds.
Contextual factor analysis (p. 16)	This section has been changed based on the advice of statisticians from the Centre for Trials Research, to ensure it reflects differences in the mode of delivery between phase one and two, as well as identifying more clearly the contextual factors we are going to consider.
Cost evaluation (p. 18)	Additional information added about how we will consider any differences in cost between face-to-face and virtual rounds.
Data protection (p. 19)	Added in a link to Cardiff University's data protection notice for research participants.
Personnel (p. 19)	[name] joined the research team in March 2020.
Timeline (p. 19-20)	Amended to reflect the addition of five new authorities and revised dates for data collection and the end of the project.
References (p. 21)	Additional references added.

Working in children's services is challenging, with workers often reporting high levels of stress and 'burn out'. Such difficulties can contribute to high rates of sickness-related absence and turnover (Ravalier, 2018). Recent Department for Education (2019) figures indicate a headcount turnover rate of 16% in the year ending September 2018, compared to a turnover rate for teachers of 9% over a similar period. Previous research has shown that the expected working life for a social worker is eight years, compared with twenty-five years for doctors and fifteen years for nurses (Curtis et al, 2010). Levels of stress may be exacerbated by limited resources, high workload and insufficient organisational support. Yet even in ideal circumstances children's services would still be a stressful place to work. Social workers and others will regularly encounter people living in very difficult situations, who have experienced abuse, neglect, poverty and social exclusion. Helping staff to provide the best possible levels of service means taking account of the nature of the work itself, and how it can create stressful emotional responses.

Schwartz Rounds is an intervention aimed at improving the psychological well-being of staff and improving the nature of care provided. There is some evidence that it works in health settings. This study will evaluate whether it improves psychological well-being and reduces staff stress in English children's services.

As set out in the previous protocol, we initially planned to work with six local authorities in total, with all of them providing Schwartz Rounds face-to-face. We expanded the study to include five additional local authorities in order to increase the sample size and the chances of avoiding a false negative result (i.e., failing to identify a positive effect on staff levels of stress caused by Schwartz Rounds). The original six authorities are referred to as phase one (of the trial), and the additional five authorities as phase two (of the trial). The plan at the outset, at the point when the five new authorities were recruited, was that they would also provide face-to-face Schwartz Rounds for their staff, in the same way the authorities in phase one had done. However, due to the Covid-19 pandemic and associated lockdowns and social distancing requirements this was not possible. Therefore, the phase two authorities will deliver virtual Schwartz Rounds (also called Team Time) instead.

Although there are no published studies that we could find which compare the effectiveness of face-to-face Schwartz Rounds with virtual Schwartz Rounds, there are studies of face-to-face counselling compared to online counselling, which tend to find similar levels of effectiveness (e.g., Barak et al, 2008; Stefanopoulou et al., 2018). This could suggest that virtual Schwartz Rounds may have a similar effect to that of face-to-face Schwartz Rounds (albeit we intend to consider this empirically as part of our exploratory analysis).

# **Intervention and Theory of Change**

Name of the intervention: Schwartz Rounds (face-to-face or virtual).

Why: To improve the psychological well-being of staff.

Who: Members of staff employed by children's services (including social workers, managers, family support workers, administrative/professional support staff and others).

Where: Local authorities in England (in phase one – Haringey, Liverpool, Nottinghamshire, Walsall, Warwickshire and West Sussex; in phase two – Bath and North East Somerset, Derby, Enfield, Leicester and Swindon).

How much: The six local authorities in phase one will hold at least six face-to-face Schwartz Rounds between May and December 2019. The five local authorities in phase two will hold at least four virtual Schwartz Rounds between November 2020 and April 2021, but ideally up to six. The original plan was for phase two authorities to also hold six face-to-face rounds (between February 2020 and September 2020), but this was not possible due to the Covid-19 pandemic.

A previous study of Schwartz Rounds in health-care settings found that attendance at four rounds was a suitable threshold for comparison with non-attendance (Maben et al., 2018). Based on this previous study, using the General Health Questionnaire-12, regular attenders (those who attended at least four rounds) experienced a 13% decrease in their chances of crossing the 'caseness' threshold, compared to a 3% decrease for non-attenders.

The same evaluation provided a description of the intervention as follows:

"Schwartz Rounds provide a regular open forum for multidisciplinary staff to come together [and] reflect on, explore and tell stories about the difficult, challenging and rewarding experiences they face when delivering care. Rounds last for 1 hour and are often held during lunch periods (with food provided). The focus is on the psychosocial, ethical and emotional issues surrounding [relationships] – and attendees are encouraged to be open and honest, and reflect, discuss and explore their experiences, thoughts and feelings. [Rounds can lead to] improved communication and teamwork between staff and [families], improved well-being, enhanced resilience [and] improved compassionate care" (Maben et al., 2018, p.14).

In children's social care, the intention is to adhere to this approach as closely as possible. Schwartz Rounds will be open to all staff in the intervention group – including social workers and other professionals and non-professionals who are directly employed to work in children's services across the trial sites (e.g., family support workers, specialist adult workers, administrative and professional support staff, etc.). This reflects the multidisciplinary nature of the rounds in healthcare settings. Staff will be notified by email, via staff newsletters and other communications, and by presentations at team meetings. Sites will also be asked to convene steering groups, and to nominate a senior champion (or Practice Lead). Each site will also have a number of trained facilitators (at least two in each LA) and an administrator to support delivery. The facilitators, administrators and Practice Leads will be identified prior to randomisation and will not formally be part of either the intervention or the control groups. The Point of Care Foundation (the licensed provider of Schwartz Rounds in the UK) will train the facilitators and Practice Leads. Facilitators and Practice Leads will also receive ongoing mentoring support from the Point of Care Foundation throughout the trial and beyond. Point of Care Foundation mentors will observe one to two rounds at each site, in order to support implementation and advise on fidelity.

Phase two local authorities will deliver Schwartz Rounds virtually but will adhere to the approach outlined above as closely as possible. Facilitators and Practice Leads will undergo specific training with the Point of Care Foundation in order to facilitate virtual rounds.

The key similarities and differences between virtual Schwartz Rounds (or Team Time) and face-to-face Schwartz Rounds, as described by the Point of Care Foundation, are as follows:

#### Similarities:

[figure not shown]
Schwartz Rounds and Team Time are run by two trained facilitators, who assist those in attendance to avoid problem solving and to focus instead on emotional containment. They are open to members of staff from different backgrounds and roles, with story tellers acting as role models for sharing narratives from an emotional and social perspective. Those in the audience interact with one another based on shared experiences and resonances with the stories. Attendance is optional and the stories and experiences shared are kept confidential. The sessions are run on a strict time frame.

#### Differences:

Schwartz Rounds and Team Time differ because Team Time is aimed at smaller groups of people, not the whole organisation. There are fewer story tellers, and a shorter timeframe for the session overall, although they may be run more frequently. The focus of the stories is on current experiences, rather than past events. Team Time relies on virtual forms of communication without physical contact and interaction, including the sharing of food (which is a key feature of Schwartz Rounds). There is typically less preparation time involved with Team Time, and other techniques may be used such as mindful breathing.

[figure not shown]
You can read more about Team Time on the Point of Care Foundation's website here.

# **Logic Model**

This logic model is based on Maben et al. (2018, p. 99). For this trial, the primary aim is to measure the effect of Schwartz Rounds in children's social care rather than to evaluate this logic model. In their report, Maben et al. (2018) suggest that Schwartz Rounds 'work' by offering staff a space in which they can share personal experiences of work. By being explicitly not a decision-making or action-oriented space, staff feel able to have different kinds of conversations about their work. By sharing personal work-related experiences with one another, staff come to recognise their shared experiences. This can be particularly powerful when senior members of staff are involved and share their stories. As staff feel more connected, they develop greater trust and empathy with one another. This in turn leads to an enhanced sense of connectedness between staff and better teamwork which leads to better psychological well-being for the staff involved.

Maben et al. (2018) identify four stages in the delivery of each round and nine context-mechanisms-outcome (CMO) configurations, detailing "what it is about [the] initiative that works, for whom and in what circumstances" (p. 95). The four stages are as follows:

The nine CMOs identified by Maben et al. (2018) are as follows:

- 1. Trust, emotional safety and containment
- 2. Countercultural/third space for staff
- 3. Storytelling
- 4. Role-modelling vulnerability
- 5. Shining a spotlight on hidden stories and roles
- 6. Self-disclosure
- 7. Contextualising service users and staff
- 8. Reflection and resonance
- 9. Group interaction

Detailed explanations of each of these CMOs can be found in Maben et al.'s report (2018, pp. 100-119).

# **Impact Evaluation**

#### **Hypotheses**

The primary hypothesis is that at the end of the trial period (at T2), GHQ-12 scores in the intervention group will be lower than in the control group.

The GHQ-12 (General Health Questionnaire) is a screening tool for identifying increased risk of anxiety, depression and related psychiatric disorders in the general population. It is suitable for all ages and is widely validated. It has been used previously with social workers in four local authorities to assess their levels of stress and general wellbeing (Antonopoulou et al., 2017).

#### Secondary hypotheses are:

[figure not shown]
- a. The proportion of GHQ-12 scores above the 'caseness' threshold (of 3) will be lower in the intervention group than in the control group at T2.
- b. The number of days of sickness-related absence during the trial period will be lower in the intervention group than in the control group at T2.
- c. Regular attendance at Schwartz Rounds will be associated with lower GHQ-12 scores compared with less regular and non-attendance.
- d. Schwartz Rounds will be considered acceptable by the staff who attend.

We will also conduct some other exploratory analyses described in the analysis plan.

[figure not shown]
# Design

The overall study design is an individually randomised control trial with group delivery of the intervention. It is a two-arm study, with an intention-to-treat intervention group and a waiting-list control, with the aim of assessing the effectiveness of Schwartz Rounds within children's social care in relation to the psychological well-being of staff.

Trial Type and Number of Arms		Randomised control trial with two arms (intention-to-treat and waiting-list control)	
Unit of Randomisation		Individual members of staff	
Stratification Variables (if applicable)		Phase (one or two)	
Primary Outcome	Variable	Psychological well-being of staff	
	Measure (instrument, scale)	GHQ-12	
Secondary Outcome(s)	Variable(s)	Sickness-related absence	
	Measure(s) (instrument, scale)	Self-report	

#### **Data collection points**

T1 data collection (GHQ-12 plus additional questions about personal and professional characteristics, views about the intervention and current forms of emotional support) will be collected electronically via Qualtrics. Links to the survey will be sent to members of children's services staff at participating sites. Participants will be asked to include their initials and day and month of birth and/or their work email addresses, so that T1 responses can be linked with sessional feedback questionnaires (see below) and T2 questionnaire responses. Raw data will be downloaded from Qualtrics to a secure Cardiff University computer for analysis via SPSS or STATA. Data from each of the participating sites will be merged together into a single database.

T2 data collection (GHQ-12 plus additional questions about other forms of emotional support utilised within the trial period and views about the intervention) will be collected in the same way as T1 data.

To minimise missing data at T1 and T2, we will work with the Local Authority sites to ensure good communication with participants and ask that two follow-up reminders are sent to participants who do not complete the surveys after the first request. We will follow up any still-missing participants directly with the LA (i.e., they will be informed of participants who have not responded and asked to send a third follow-up request). We will also offer an incentive for completing the surveys at T1 and T2, entering each participant who does so into a draw to win £250, with one winner selected from each LA (Nb. One of the local authorities in phase one – Liverpool – opted out of this prize draw).

Anonymised versions of the entire dataset will be stored at Cardiff University for five years after publication of findings.

#### Randomisation

A researcher not otherwise involved in the study will use staff lists provided by the LAs to create equal-sized intervention and waiting-list-control groups, with staff randomly allocated to each group.

To achieve this, each LA will provide a pseudonymised list of staff working in children's services (e.g., based on employee numbers). Using Excel's randomisation feature a random number will be generated for each employee, the list will then be sorted from smallest to largest, and then split in half at the median value to create two equal sized groups (plus or minus one, if the list contains an odd number of staff; Zelen, 1979). Each LA will then be given a list of staff in each group, which they can re-identify and circulate, so as to ensure that members of staff know which group they are in (this information will not be shared with staff until after the T1 survey has been closed).

The control group will be asked not to attend Schwartz Rounds during the trial period but will continue to receive 'business as usual' support from their authorities. The intervention group will also continue to receive 'business as usual' support but will also be invited to attend Schwartz Rounds (whether virtually or face-to-face). For social workers, 'business as usual' support will likely include monthly one-to-one supervision with a line manager. In some sites, this may also include group supervision, reflective practice groups or other group-based interventions. Some sites may also provide staff with counselling services where this is required. For non-social work staff, 'business as usual' support may include some or none of these elements. We will ask staff about what other support they have available and what other support they have accessed as part of the T2 survey.

Direct contamination (by members of the control group attending Schwartz Rounds) will be measured via sessional feedback questionnaires. The extent and significance of indirect contamination (by members of the intervention group talking about the intervention outside of rounds) will be explored via focus groups at T2.

Analysts will be blinded to group allocation in relation to GHQ-12 and group-level absence data.

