Sessional feedback questionnaires will be handed out on paper to every attendee at a face-to-face Schwartz Round and distributed via Qualtrics to each attendee at a virtual Schwartz Round. These forms are used widely in Schwartz Round studies and ask people to report their subjective experience of having attended. We will also use these as a record of attendance, by asking participants to include their initials and day and month of birth. We will also ask each LA for a record of how many people attended each session. The paper forms will be collected back in at the end of each round and collected from each site by a member of the research evaluation team. The data from the forms (both paper and online) will be entered into SPSS. The SPSS database will be stored securely on a Cardiff University computer. Paper copies are kept in a secure locked cupboard at Cardiff University, accessible only to members of the evaluation team.

Focus groups and interviews will be held for each site, either in the local authority offices or online. Interviews and focus groups will be conducted and facilitated by members of the evaluation team. They will be audio recorded using digital Dictaphones. Recordings will be uploaded to a secure Cardiff computer and deleted from the Dictaphone as soon as reasonably possible. Interviews and

focus group recordings will then be transcribed and analysed using Nvivo, based on a coding framework developed from the relevant research questions.

To help compare the experience of attending and providing face-to-face and virtual rounds, we will also conduct interviews with key informants and staff members in two phase one authorities (who provided face-to-face rounds previously and during the Covid-19 associated lockdown have switched to virtual rounds).

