# **Ethics & Participation**

Ethical approval for the study has been given by the School of Social Sciences, Cardiff University.

Staff in participating local authorities will be given information and consent sheets about the study. Each local authority will then implement an individual communication strategy, to ensure staff are aware of the intervention, involving a mixture of email bulletins, intranet blogs and staff briefing sessions. Written consent will be obtained from each attendee at each Schwartz Round (to ensure that irregular attendees, who may not have attended the first round or any round before, are also given the opportunity to consent or not). This will be done as part of the sessional feedback questionnaire. Questionnaires will be given out to each member of staff upon arrival at the round by one of the facilitators or the Practice Lead. At the end of each round, staff will be reminded to fill in the questionnaire and return it to the facilitators on their way out. If staff have already completed a consent form, they will not need to fill in another one on subsequent rounds but may choose to do so as part of completing the feedback questionnaire.

Each member of staff in the department will also be emailed a T1 and T2 questionnaire (including the GHQ-12). Completion of the questionnaire will be voluntary. This will be made clear in the invitational email and at the start of the questionnaire itself.

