#### **Data Protection**

We will only collect and process data in order to address our research questions. In all circumstances, the identities of individuals taking part in the study and the data they provide will be kept confidential and will only be used for research purposes. Participants will be informed of their right not to take part in the study, either by not attending Schwartz Rounds or by attending without taking part in data collection activities.

Data will be processed only when the data subject has given consent to the processing of his or her personal data for the specific purpose of conducting this trial.

All data collected will be stored securely on Cardiff University computers.

Cardiff University's research data protection notice can be read – here.

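### Control-arm attendance at Rounds is recorded only on a feedback form that attendees may decline, so direct contamination is likely to be under-counted; one T2 question would give a better measure

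*Protocol*

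**What the plan says.** The Randomisation section of the Protocol gives controls an instruction, "The control group will be asked not to attend Schwartz Rounds during the trial period", and names one measure of whether they followed it: "Direct contamination (by members of the control group attending Schwartz Rounds) will be measured via sessional feedback questionnaires". Indirect contamination is left to focus groups and is not at issue here.

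Five other statements bear on how well that measure can work:

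- **Key on the form.** Implementation and Process Evaluation says of the feedback forms: "We will also use these as a record of attendance, by asking participants to include their initials and day and month of birth". No item recording trial arm is described.
- **Key on the surveys.** Data collection points asks survey respondents for "initials and day and month of birth and/or their work email addresses".
- **Right to decline.** Data Protection says that staff may stay out of the study "either by not attending Schwartz Rounds or by attending without taking part in data collection activities". Ethics & Participation puts the consent request on the same form: irregular attendees "are also given the opportunity to consent or not). This will be done as part of the sessional feedback questionnaire". The form goes back to the facilitators.
- **Head count.** "We will also ask each LA for a record of how many people attended each session". This is a total; a split by arm is not requested.
- **Allocation list.** "Each LA will then be given a list of staff in each group, which they can re-identify and circulate". The list is pseudonymised, for example by employee number.

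Under Secondary Analysis, the fraction of sessions attended is the treatment variable in a two-stage least squares CACE, with assignment as the instrument. The T2 survey content listed under Data collection points includes no question on Rounds attended.

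**The concern.** Staff are randomised individually within the same departments, and Rounds are advertised by email, newsletter and briefing, so some control attendance is possible. The plan recognises this and sets out to measure it. But the measure depends on the cooperation of the people it is meant to detect. A control member at a Round was asked not to be there, may attend without giving data, and would return the form to a facilitator in an authority that holds the allocation list.

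Two things depend on the count. The first is how the primary result is read: if control attendance is reported as low because forms were not returned, a diluted null will be taken as a clean one. The second is the CACE, whose first stage is the arm difference in recorded attendance.

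**Working it through.** **The plan's own figures.** The Protocol gives no contamination rate, no form-return rate and no contamination allowance in the sample size table. There is therefore no stated figure on this point to reproduce, and every rate below is an assumption.

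**Step 1: direction of error in the control count.** A control attendance is counted only if the attendee returns a form and the form can be tied to the control arm. With true control attendance c and the share of it captured q, the recorded attendance is c × q.

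| c | q | recorded |
|---|---|---|
| 5% | 0.8 | 4% |
| 5% | 0.5 | 2.5% |
| 10% | 0.8 | 8% |
| 10% | 0.5 | 5% |
| 10% | 0.3 | 3% |

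False matches on initials and birthday aside, c × q cannot exceed c. It equals c only if every control attendee returns a linkable form.

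**Step 2: linkage.** The described key on the form is initials and birthday. A survey respondent may give only a work email, which the form is not described as asking for, so that person's form would not match. How a form or survey is tied to a list held by employee number is not described.

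**Step 3: does the head count repair this?** Head count minus forms returned shows how many attendees returned nothing. It does not show which arm they belong to.

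**Step 4: why the reading of a null depends on c.** The planned 238 per arm is close to the one-sided calculation without covariate for 0.23 SD: 2 × (1.645 + 0.842)² / 0.23² = 234. Power at 238 per arm is 0.81. If contamination dilutes the effect to 0.23 × (1 − c), power is 0.77 at c = 5% and 0.73 at c = 10%. This dilution occurs whether or not attendance is recorded; poor recording only hides it.

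**Step 5: the CACE.** The estimate is the intention-to-treat difference divided by the arm difference in recorded attendance. Let true attendance be aI and aC, with shares qI and qC captured:

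estimated/true = (aI − aC) / (aI × qI − aC × qC)

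Take aI = 0.30, aC = 0.10 and qC = 0.3. The true difference is 0.20.

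- qI = 1: 0.20 / (0.30 − 0.03) = 0.20 / 0.27 = 0.74, so the CACE is 26% too small.
- qI = 0.6: 0.20 / (0.18 − 0.03) = 0.20 / 0.15 = 1.33, so it is 33% too large.
- Break-even: 0.30 × qI − 0.03 = 0.20, so qI = 0.23 / 0.30 = 0.77.

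With these inputs the CACE is too small when more than about 77% of intervention attendance is captured and too large when less is.

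**The case against.** The strongest reply is that the damage is limited. The primary analysis uses assignment only, so no estimate, standard error or test there changes. The form itself is not reproduced, so it may carry more than the items described. Matching rules may sit in a document that is not shown. Email was added to the surveys as an optional aid to matching, and how many respondents would give email alone is unknown. All of this stands and keeps the point minor. It does not restore the measure: no analysis plan can recover an attendance that was never recorded, and the right to attend without giving data is explicit.

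A reader might infer three stronger things that the document does not support:

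- **That the CACE is pulled towards zero.** This needs intervention attendance to be fully counted. Mismatched keys and the right to decline apply to both arms; only a control member's reluctance is specific to one arm.
- **That the 50% and 75% loss scenarios in the sample size table drive the under-count.** Those are scenarios for follow-up loss. The primary model and the CACE need a T2 outcome, so the controls who are analysed did answer T2. Forms from controls without T2 data do not bias the first stage.
- **That a count by arm is already to hand.** Someone would have to identify each attendee against the allocation list, including those who declined data collection, and consent limits what may be processed. No log-in record for virtual Rounds is mentioned.

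**Conclusion.** The point holds as a minor one. The only named measure of direct contamination is likely to under-count control attendance. The direction follows from the form being declinable and from the reason a control member has to decline it. The size cannot be computed from the Protocol.

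The intention-to-treat estimate is untouched by the recording error; what suffers is the assurance that a null result is free of contamination. The CACE attendance variable is mismeasured with bias of unknown sign. The ratios 0.74 and 1.33 show that the sign can change; they are not forecasts, and they rest entirely on the assumed attendance and capture rates.

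**What to change.** 1. **Data collection points:** add one T2 question, to all staff in both arms, on how many Rounds they attended during the trial period. Use it together with the forms to report control attendance, and as a sensitivity analysis for the CACE attendance variable. It reaches the people who enter those analyses and does not depend on a returned form.
2. **Data collection points and Implementation and Process Evaluation:** ask for the same identifiers on the surveys and the feedback form.
3. **Optional:** where an authority can readily do so, it may supply the existing head count split by arm, as an aggregate cross-check. This covers all staff and not only T2 respondents, so it will not match the first stage exactly.

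The cost is one more survey item and a small change to the identifier fields. Self-reported attendance has recall and reporting error, and a control member may under-report there too. Phase one data collection is complete and cannot benefit. In phase two, T2 is planned for March and April 2021, after this December 2020 version, so the question can still be added. Phase two T1 and the first virtual Rounds were scheduled for October and November 2020, so matching identifiers can help only T2 and the remaining Rounds.
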